Endocrine therapies, such as letrozole and fulvestrant, are a mainstay of HR+ breast cancer treatment, sometimes in combination with other therapies. The PALOMA-1 trial evaluated palbociclib, a cyclin-dependent kinase 4 and 6 (CDK4/6) inhibitor, in combination with letrozole in patients with HR+/HER2-ABC/MBC. Palbociclib combination therapy with letrozole demonstrated median progression-free survival (PFS) of 20.2 months versus 10.2 months in patients receiving letrozole and placebo (5). These results were confirmed by the success of the phase III PALOMA-2 study, in which palbociclib and letrozole combination treatment demonstrated greater median PFS than letrozole and placebo (24.8 months and 14.5 months, respectively) (6). In cases of disease progression despite initial endocrine therapy, the PALOMA-3 trial demonstrated that palbociclib combination with fulvestrant resulted in median PFS of 9.2 months compared to 3.8 months in those receiving fulvestrant and placebo (4,7). Currently, palbociclib is indicated for use in combination with any aromatase inhibitor or fulvestrant for those with HR+/HER2- ABC/MBC (8).

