9.5. Study size

All female patients who are ≥ 18 years of age and are diagnosed with HR+/HER2- ABC/MBC at Sinai Health during the study period will be included in the study. It is estimated that there will be approximately 300 diagnoses of ABC/MBC within the study period at Sinai Health, of which approximately 180 will be HR+/HER2-. All analyses are descriptive in nature and so sample size calculations are not applicable.

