2.2 STUDY OBJECTIVES

The following objectives are taken from the protocol:

Primary objective

- *To characterize real world treatment patterns among patients with HR+/HER2- ABC/MBC receiving palbociclib combination treatment (non-steroidal AI (NSAI) [letrozole or anastrozole], or fulvestrant)*

Secondary objectives

- *To determine pre- and post-CDK4/6i treatment patterns and sequencing in ABC/MBC patients.*

CCI

PFIZER CONFIDENTIAL

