4.3 OTHER ANALYSIS SET

The primary objective will include only patients who received at least one dose of Palbociclib during the study period.

The secondary and **CCI** objectives will include all patients in the full analysis set.

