7.2 STATISTICAL ANALYSES

Treatment patterns and changes:

Treatment patterns among patients with HR+/HER2- ABC/MBC receiving Palbociclib will be analysed as the primary objective of this study. This analysis will be conducted in all patients who have received Palbociclib combination treatment. Subgroup analyses on patients who are likely to be pre-menopause might also be conducted if applicable. This analysis will be descriptive in nature and is subject to modification based on sample size and final data specifications. No statistical tests will be utilized. Continuous and categorical variables will be described using methods outlined in Section 7.1 of this document. Sankey diagrams and/or bar charts may also be used to illustrate sequencing and changes in treatment patterns if appropriate. The above-mentioned analyses will use the following or similar R packages: 'tables', 'ggplot', and 'networkD3'.

Type	Objective	Endpoint	Population	Statistical Method/Test	Covariates used	Method of adjustment for missing values	Role of the analysis related to study objectives
Table	1	Not applicable	- All patients who have received Palbociclib	Descriptive stats	Systemic therapies	Missing data will be summarized in table.	To describe treatment patterns during

PFIZER CONFIDENTIAL

			combination treatment. - Pre-menopausal patients ^a			Missing days from dates will be handled as per section 6 of this document.	study period.
Bar chart	1	Not applicable	- All patients who have received Palbociclib combination treatment. - Pre-menopausal patients ^a	Descriptive stats	Systemic therapies	Missing data will be excluded. Missing days from dates will be handled as per section 6 of this document.	To illustrate changes in treatment patterns by year.
Sankey diagram	1	Not applicable	- All patients who have received Palbociclib combination treatment. - Pre-menopausal patients ^a	Descriptive stats	Systemic therapies	Missing data will be excluded. Missing days from dates will be handled as per section 6 of this document.	To illustrate sequencing of treatments.

^a Patients who are potentially pre-menopausal may be analyzed as a subgroup for this objective. Please refer to section 4.4 of this document for further details about how this group is defined.

Pre- and Post-CDK treatment patterns:

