Age	N Mean (SD) Median Q1, Q3 Minimum-Maximum		
Sex	Female Male Unknown		
ECOG	0 1 2 3 4 Unknown		
Organ level metastatic site	Bone Brain Lungs Liver		
Number of metastatic sites	0 1 2 3 4		
Comorbidities	Atrial fibrillation Hypertension Coronary Artery Disease/Myocardial infarction/Angina Diabetes Mellitus Stroke		
Tumour stage at diagnosis	I II III IV Unknown		
Tumour grade	1		

PFIZER CONFIDENTIAL

2		
3		
Unknown		
Tumour histology		
Lobular Carcinoma		
Ductal carcinoma		
Mixed		
DCIS		
LCIS		
Other		
Unknown		
ER Receptor status		
Positive		
Negative		
Unknown		
PR Receptor status		
Positive		
Negative		
Unknown		

^a Defined as patients who were diagnosed between March 10, 2019 – March 10, 2020.

^b Defined as patients who were diagnosed between March 11, 2020-March 11, 2021.

Treatment patterns and changes:

Table 6: Line 1 Treatment Patterns in patients who received Palbociclib

Variables	Overall (N=) ^a	Pre-menopausal patients (N=) ^b
Chemotherapy N, Mean Tx duration (SD)		
Chemo drug 1, n (%)		
Chemo drug 2, n (%)		
...		
Targeted therapy N, Mean Tx duration (SD)		
Targeted drug 1, n (%)		
Targeted drug 2, n (%)		
...		
...(Any other Class of therapy observed)		

^a Includes all patients who received Palbociclib

^b Includes patients who received Palbociclib and who are potentially in pre-menopause. Please refer to section 4.4 of this document for further details about how this group is defined.

Treatment patterns and changes in patients who received Palbociclib:

[figure not shown]

Figure 1: Classes of treatments over time in patients who received Palbociclib. Similar plots will be created for all lines of therapy. Stacked bar charts can be either absolute values (as shown) or percentages, as required.

Figure 2: Sankey Diagram of treatment of patients who received Palbociclib

Treatment patterns and changes in patients who received Palbociclib who are potentially in pre-menopause.

[figure not shown]
Figure 3: Classes of treatments over time in patients who received Palbociclib who are potentially in pre-menopause. Please refer to Figure 1 for reference as to how bar charts will look. Similar plots will be created for all lines of therapy.

GER CONFIDENTIAL

Figure 4: Sankey Diagram of treatment of patients who received Palbociclib who are potentially in pre-menopause

PFIZER CONFIDENTIAL

Pre and Post-CDK treatment patterns:

Table 7: Pre and post-CDK treatment patterns and sequencing in patients

	Pre-CDK ^a			Post-CDK ^b		

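### The only treatment-pattern table for the primary objective stops at Line 1, so a palbociclib regimen started later is counted in its denominator but appears in none of its rows

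*SAP*

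**What the plan says.** - **Objective.** SAP 2.2 sets the primary objective as treatment patterns among patients "receiving palbociclib combination treatment (non-steroidal AI (NSAI) [letrozole or anastrozole], or fulvestrant". The regimen of interest is a pair of drugs, and three partners are named.
- **Population.** SAP 4.3 states: "The primary objective will include only patients who received at least one dose of Palbociclib during the study period". Line of therapy plays no part in this definition.
- **Purpose of the table.** The SAP 7.2 grid plans a table, a bar chart and a Sankey diagram for objective 1. The table's role begins "To describe treatment patterns during" and goes on to name the study period. The text above the grid makes the two figure types optional.
- **The shell.** In SAP section 8 the matching table is "Table 6: Line 1 Treatment Patterns in patients who received Palbociclib". The footnote to its overall column reads "Includes all patients who received Palbociclib". Its rows are placeholders for drugs within chemotherapy, targeted therapy and any other class seen. Treatment duration appears only in the class header rows.
- **The data.** Protocol Table 1 and SAP 5.5 list start and stop dates, combination therapies and line of therapy among the variables to be extracted.

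**The concern.** The table's population is defined by palbociclib at any line, but its content is limited to the first line. For a woman who had endocrine therapy or chemotherapy first and palbociclib second, Table 6 shows only the earlier drugs.

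The basic descriptive question behind the primary objective is which palbociclib combination was given, in which line, and for how long. If the shell is followed as written, no planned table for that objective answers it for later-line starters. Women who receive palbociclib with fulvestrant may be more exposed to this than others: Protocol section 7 introduces the trial evidence for that pair with "In cases of disease progression despite initial endocrine therapy". The same section gives the current indication without any limit by line, so this is a likely direction and not a measured one.

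**Working it through.** The protocol says "All analyses are descriptive in nature and so sample size calculations are not applicable", and for objective 1 SAP 7.2 says "No statistical tests will be utilized". No power or error-rate figure is in play, so the check is to go through the shells in SAP section 8 and see what each can show.

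| Shell | Serves | Population | Lines covered |
|---|---|---|---|
| Table 6 | Objective 1 | All palbociclib recipients, plus a pre-menopausal column | Line 1 |
| Figures 1 and 3 | Objective 1 | As Table 6 | All lines, by class |
| Figures 2 and 4 | Objective 1 | As Table 6 | Sequence, as Sankey diagrams |
| Table 7 | Objective 2 | Starters in January to May 2016 and January to May 2019 | Lines 1 to 3 |
| Table 8 | Objective 2 | Overall | Therapies after a CDK4/6 inhibitor |
| Tables 9 and 10 | Exploratory, by responder type | All, and pre-menopausal | Line 1 |
| Table 11 | Exploratory, COVID-19 | Diagnosed in the year before or the first year of the pandemic | Line 1 |
| Table 12 | Exploratory, COVID-19 | All, split by start date | Lines 1 to 3 |

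Tables 1 to 5 hold baseline characteristics only.

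**Step 1: count for objective 1.** There is one treatment-pattern table, it covers one line, and it specifies no combination row. Two tables have columns for Lines 1 to 3 (Tables 7 and 12), and neither serves objective 1.

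**Step 2: follow one patient.** Take a woman with an aromatase inhibitor in Line 1 and palbociclib plus fulvestrant in Line 2. She meets SAP 4.3 and adds one to N in Table 6. Her aromatase inhibitor goes in a Line 1 row. Her palbociclib, her fulvestrant and her time on them go in no row. If palbociclib has its own Line 1 row, subtracting that count from N gives roughly how many women started it later. It does not give the line, the partner or the duration.

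**Step 3: are such women expected?** SAP 4.1 requires treatment with a CDK4/6 inhibitor, and SAP 4.3 applies the full analysis set to the secondary objective. SAP 4.4 nevertheless defines a subgroup starting systemic therapy in January to May 2016, before CDK4/6 inhibitors were introduced. Any member of it received the inhibitor after starting something else, normally in a later line. So the SAP itself anticipates later-line starters. It does not say how many, or whether their inhibitor was palbociclib.

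**Step 4: bound the cohort.** The amendment tables give the reason for the 2023 change as a sample below 30% of the planned 180. 0.30 × 180 = 54, so the whole CDK4/6 inhibitor cohort is below 54. Palbociclib recipients are some or all of it, and later-line starters are some part of those.

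**The case against.** The strongest defence has four parts.

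1. **Later lines are planned for objective 1.** Figure 1 is to be repeated for every line, in absolute values or percentages, and Figure 2 shows sequence. This stands in part: later lines are not absent. But the bar charts are by class, both figure types are optional, and missing data are excluded from them. The Sankey's nodes cannot be seen in the text available, so whether it shows drugs or regimens is unknown. Neither figure is specified to give n (%) or duration by regimen.
2. **The rows are placeholders.** A reader might infer that Table 6 separates palbociclib from its partner for good. The documents do not support that. The SAP does not say how a combination fills a row, a regimen row is not excluded, and a Line 1 endocrine partner can appear under the catch-all class. What can be said is that no combination row is specified.
3. **A non-palbociclib first line belongs in the table.** This stands. It is part of the treatment pattern of a palbociclib patient, and the title describes it correctly. The fault lies in what is left out.
4. **The shells may be modified.** SAP section 8 allows changes for data availability, sample size and final data specifications. It also calls the list complete as to desired analyses. Since line and combination are extraction variables, none of those reasons accounts for stopping at Line 1.

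A reader might also infer that the primary objective alone was restricted in this way. It was not: Tables 9 and 10 are confined to Line 1, and so is the treatment section of Table 11.

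**Conclusion.** The point holds as a gap in the planned display for the primary objective. Table 6 counts every palbociclib recipient, describes Line 1 only, specifies no row for the named combinations and gives duration by class. No other planned table fills the gap for that objective. This follows from the text and needs no numerical assumption.

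The number of women affected cannot be given. A reader might size it from the Canadian chart review cited in Protocol section 7, where 33 of 212 + 33 = 245 women (13.5%) received the fulvestrant combination. That figure measures partner drug, not line, and nothing in the documents equates the two. The ceiling of 54 does not yield an estimate either, because it covers users of any CDK4/6 inhibitor and not palbociclib recipients alone.

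The consequence is incomplete reporting. No test or decision rests on Table 6, and nothing is lost beyond recovery, because the variables are extracted either way. It is still worth correcting before the tables are produced, since it concerns the main numeric display for the primary objective.

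**What to change.** Change the Table 6 shell in two ways.

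- Give it columns for Lines 1, 2 and 3, in the layout of Tables 7 and 12.
- Add a block for the palbociclib-containing line, with rows for palbociclib + letrozole, + anastrozole, + fulvestrant and + other/none. Show each by the line in which it was started, with n (%) of all palbociclib recipients and time on that regimen. The last row is needed because SAP 4.3 admits anyone with a single dose, while the objective speaks of combinations.

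State in a footnote how a woman with palbociclib in more than one line is counted, and how regimens still running at the end of the study period (01 October 2021) enter the duration. Keep the pre-menopausal column where numbers allow, as SAP 4.4 already provides.

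The cost is a change to one SAP shell and its programming, with no new data. The drawback is sparse cells. Four partner rows × 3 lines × 2 columns = 24 cells for a cohort below 54, so many will be small or empty. Lines 2 and 3 could be pooled in the added block if that proves unreadable.

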9.3. Variables

Table 1. List of study variables to be extracted (where feasible)

Variable	Role	Data source(s)	Operational definition
Patient demographics	Baseline characteristic, potential confounder, sub-group identifier	Patient EHR	
• Date of birth• Sex• Date of death
Clinical characteristics	Baseline characteristic, potential confounder, sub-group identifier	Patient EHR	
• Date of ABC/MBC diagnosis• Age at ABC/MBC diagnosis (years)• ECOG performance score at index date (0, 1, 2, 3, 4)• ESAS• Date of last follow-up• Organ level metastatic sites (bone, brain, lungs, liver; number of sites)• Tumour stage at initial breast cancer diagnosis (I, II, III, IV, Unknown)• Tumour grade• Tumour histology• ER and PR receptor status (Positive, Negative, Unknown)• HER2 status (Positive, Negative, Unknown)• Concomitant LHRH agonists
Comorbidities	Baseline characteristic, potential confounder, sub-group identifier	Patient EHR	
• Atrial fibrillation• Hypertension• Coronary Artery Disease/Myocardial infarction/Angina• Diabetes Mellitus• Stroke
Treatments	Exposure	Patient EHR	
• Systemic Therapies (therapy start and stop date including combination therapies, and line of therapy)• Surgeries• Radiation Treatment
Clinical outcomes	Outcome	Patient EHR	
• TTNT1• TTNT2• TTC• Overall Survival (landmark 3y)

ECOG, Eastern Cooperative Oncology Group; EHR, Electronic Health Record; ER, Estrogen Receptor; ESAS, Edmonton Symptom Assessment System; HER2, Human Epidermal Receptor Growth Factor 2; LHRH, Luteinizing Hormone-Releasing Hormone; PR, Progesterone Receptor; TTC, time from date of ABC/MBC to starting chemotherapy; TTNT1, length of treatment for the first line; TTNT2, length of treatment for the second line

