9.7. Data analysis

Detailed methodology for summary and statistical analyses of data collected in this study will be documented in a statistical analysis plan (SAP), which will be dated, filed and maintained by the sponsor. The SAP may modify the plans outlined in the protocol; any major modifications of primary endpoint definitions or their analyses would be reflected in a protocol amendment. Statistical analyses will be performed by PPD. The data will be analyzed using R (version and packages will be detailed in final SAP).

Descriptive analyses will be performed to summarize patients' baseline characteristics and outcomes of interest across the study cohort. Continuous variables will be described by the number of patients with valid/non-missing observations using mean, standard deviation (SD), minimum, maximum and quantiles (Q1, median, Q3). Categorical variables will be described by frequencies and related percentages. Number of missing observations will be reported for all variables. Time to event will be described using unadjusted Kaplan-Meier chart that will visually estimate the distribution of times to some events (i.e. progression), and will take into account those patients for which the event has not as yet occurred. Numbers at risk, cumulative incidence and survival medians will be reported for each curve. Endpoint definitions and how patients are censored for each endpoint will be further described in the SAP. Visualizations may be used to further describe treatment patterns, patient journeys, and other outcomes of interests if appropriate. The above planned data analyses are descriptive in nature and all subject to modification based on sample size and final data specifications. No inferential statistical analyses will be conducted.

PFIZER CONFIDENTIAL

Missing data will be excluded on a case by case basis and will not be imputed. This will mean that each table will not necessarily be based on the same number of patients.

CCI

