4 ANALYSIS SETS/POPULATIONS

4.1 FULL ANALYSIS SET

Inclusion criteria

Patients must meet all of the following inclusion criteria to be eligible for inclusion in the study:

1. *≥ 18 year old female*
2. *HR+/HER2- breast cancer diagnosis with confirmed metastatic or advanced disease*
3. *Diagnosed with ABC/MBC between 01 January 2016 and 01 July 2021*
4. *Treatment with CDK4/6 inhibitor*

Exclusion criteria

Patients meeting any of the following will not be included in the study:

1. *Patient does not have ABC/MBC*
2. *Patient has indicated HR- or HER2+ status*
3. *Patient received a CDK4/6i as part of a clinical trial*

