5.5 ENDPOINTS

Variable	Role	Data source(s)	Operational definition
Patient demographics	Baseline characteristic, potential confounder, subgroup identifier	Patient EHR	
• Date of birth• Sex• Date of death
Clinical characteristics	Baseline characteristic, potential confounder, subgroup identifier	Patient EHR	
• Date of ABC/MBC diagnosis• Age at ABC/MBC diagnosis (years)• ECOG performance score at index date (0, 1, 2, 3, 4)• ESAS• Date of last follow-up• Organ level metastatic sites (bone, brain, lungs, liver; number of sites)• Tumour stage at initial breast cancer diagnosis (I, II, III, IV, Unknown)• Tumour grade

PFIZER CONFIDENTIAL

			
 • Tumour histology • ER and PR receptor status (Positive, Negative, Unknown) • HER2 status (Positive, Negative, Unknown) • Concomitant LHRH agonists
Comorbidities	Baseline characteristic, potential confounder, subgroup identifier	Patient EHR	
 • Atrial fibrillation • Hypertension • Coronary Artery Disease/Myocardial infarction/Angina • Diabetes Mellitus • Stroke
Treatments	Exposure	Patient EHR	
 • Systemic Therapies (therapy start and stop date including combination therapies, and line of therapy) • Surgeries • Radiation Treatment
Clinical outcomes	Outcome	Patient EHR	
 • TTNT1 • TTNT2 • TTC • Overall Survival (landmark 3y)

ECOG, Eastern Cooperative Oncology Group; EHR, Electronic Health Record; ER, Estrogen Receptor; ESAS, Edmonton Symptom Assessment System; HER2, Human Epidermal Receptor Growth Factor 2; LHRH, Luteinizing Hormone-Releasing Hormone; PR, Progesterone Receptor; TTC, time from date of ABC/MBC diagnosis to starting chemotherapy; TTNT1, length of treatment for the first line; TTNT2, length of treatment for the second line

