7 STATISTICAL METHODOLOGY AND STATISTICAL ANALYSES

7.1 STATISTICAL METHODS

The following analyses are expected to be conducted in R.

Analyses for continuous Data

Continuous variables will be described by the number of patients with valid/non-missing observations using mean, standard deviation (SD), quantiles (Q1, median, Q3), minimum and maximum.

Analyses for Categorical Data

Categorical variables will be described by frequencies and related percentages.

Analyses for time to event end points.

Time to event variables will be analyzed using Kaplan-Meier curves (TTNT1, TTNT2, TTC, OS). Numbers at risk and cumulative incidence will be reported for each curve.

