7.2.2 Summary of all Analyses

Outcome	Analysis Set	Supports Protocol Objective Number	Subgroup	Statistical Method	Strata	Missing Data
Baseline Characteristics	All patients	1	None	Descriptive Stats	None	Missing data will be summarized in table. Missing days from dates will be handled as per section 6 of this document.
Treatment patterns	- All patients who have received Palbociclib combination treatment.	1	Pre-menopausal patients ^a	Descriptive stats, Bar charts, Sankey Diagram	None	Missing data will be summarized in table and excluded from figures. Missing days from dates will be handled as per section 6 of this document.
Treatment patterns and sequencing pre and post CDK	- All patients	2	-Pre-CDK subgroup	Descriptive stats,	None	Missing data will be summarized in table. Missing

PFIZER CONFIDENTIAL

			-Post-CDK subgroup	Bar charts,		days from dates will be handled as per section 6 of this document.
Treatment duration (TTNT1/TTNT2)	- All patients	Exploratory	Premenop ausal patients ^a	KM Curve	Systemic therapies	Missing data will be excluded. Missing days from dates will be handled as per section 6 of this document.
Time to chemotherapy (TTC)	- All patients	Exploratory	Premenop ausal patients ^a	KM Curve	Systemic therapies	Missing data will be excluded. Missing days from dates will be handled as per section 6 of this document.
Overall Survival	- All patients	Exploratory	Premenop ausal patients ^a	KM Curve	Systemic therapies	Missing data will be excluded. Missing days from dates will be handled as per section 6 of this document.
Impact of COVID-19	- All patients	Exploratory	- Patients diagnosed one year before and within first year of the pandemic	Descriptive Stats, KM Curve, Bar charts, Sankey Diagram	None	Missing data will be excluded. Missing days from dates will be handled as per section 6 of this document.

^a Patients who are potentially pre-menopausal are included in this subgroup. Please refer to section 4.4 of this document for further details about how this group is defined.

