	Line 1	Line 2	Line 3	Line 1	Line 2	Line 3
Chemotherapy N, Mean Tx duration (SD)						
Chemo type 1, n (%)						
Chemo type 2, n (%)						
...						
Targeted therapy N, Mean Tx duration (SD)						
Targeted type 1, n (%)						
Targeted type 2, n (%)						
...						
...						

^a Defined as treatment started between January 2016-May 2016^b Defined as treatment started between January 2019- May 2019

Table 8: Sequencing of therapies after CDK 4/6 inhibitor

[figure not shown]
	Overall (N=)
Post-CDK received in L1	
Medicinal product name 1, n (%)	
Medicinal product name 2, n (%)	
...	
Post-CDK received in L2	
Medicinal product name 1, n (%)	
Medicinal product name 2, n (%)	
...	
Post-CDK received in L3	
Medicinal product name 1, n (%)	
Medicinal product name 2, n (%)	
...	

Bar charts

Figure 5: Classes of treatments over time in all patients. Please refer to Figure.1 for reference as to how bar charts will look. Similar plots will be created for all lines of therapy.

PFIZER CONFIDENTIAL

Time to event analyses in all patients:

Figure 6: TTNT1 in all patients by type of treatment

Figure 7: TTNT2 in all patients by type of treatment

Figure 8: TTC in all patients by type of treatment

Figure 9: Overall Survival in all patients by type of treatment

Table 9: Length of Line 1 treatment in short term vs long term responders

Variables	Short term responders (n=) ^a	Long term responders (n=) ^b
Chemotherapy N, Mean Tx duration (SD)		
Chemo type 1		
N		
Mean (SD)		
Median		
Q1,Q3		
Minimum-Maximum		
Chemo type 2		
N		
Mean (SD)		
Median		
Q1,Q3		
Minimum-Maximum		
...		
Targeted therapy N, Mean Tx duration (SD)		
Targeted type 1		
N		
Mean (SD)		
Median		
Q1,Q3		
Minimum-Maximum		
Targeted type 2		
N		
Mean (SD)		
Median		
Q1,Q3		
Minimum-Maximum		
...		

^a Defined as those who are on first line therapy for up to 3 to 6 months

^b Defined as those who are on first line therapy for more than 6 months

Time to event analyses in pre-menopausal patients:

Figure 10: TTNT1 in patients who are potentially in pre-menopause by type of treatment

Figure 11: TTNT2 in patients who are potentially in pre-menopause by type of treatment

Figure 12: TTC in patients who are potentially in pre-menopause by type of treatment

Figure 13: Overall Survival in patients who are potentially in pre-menopause by type of treatment

Table 10: Length of Line 1 treatment in short term vs long term responders in pre-menopausal patients^a

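### Overall survival is to be plotted by type of treatment with no visible rule fixing the type at the start of the survival clock, so the curves can separate with no treatment effect

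*SAP*

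**What the plan says.** SAP section 8 lists two survival displays split by treatment: "Figure 9: Overall Survival in all patients by type of treatment" and "Figure 13: Overall Survival in patients who are potentially in pre-menopause by type of treatment". In SAP 7.2.2 the OS row covers all patients, is labelled exploratory, uses a Kaplan-Meier curve and names the strata only as "Systemic therapies". Protocol 9.7 confirms that there is no adjustment: "Time to event will be described using unadjusted Kaplan-Meier chart".

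Two other features matter.

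- Treatment is recorded as a sequence. SAP 5.5 lists, for systemic therapies, "therapy start and stop date including combination therapies, and line of therapy", and the shell for Table 7 runs over Lines 1 to 3. One woman can have several types.
- Entry to the full analysis set (SAP 4.1) requires "Treatment with CDK4/6 inhibitor", with no line stated.

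Other groupings in section 8 (responder type, pre- and post-CDK period, COVID-19 period) carry a definition in a footnote or caption. Figures 9 and 13 carry none. Appendix heading A1.2, on further endpoint definitions, has no text below it. SAP 5.1 and much of the time-to-event text and table in 7.2 are redacted.

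**The concern.** TTNT1 and TTNT2 each belong to one line, so the type of treatment can be known when their clock starts. Overall survival belongs to no line. If the type is settled by something that happens after the OS clock starts, membership of a curve depends partly on having lived long enough to qualify. Two natural readings have this flaw.

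- **Any therapy received.** A woman given chemotherapy at Line 3 joins the chemotherapy curve only because she reached Line 3. Every woman is also in the CDK4/6 inhibitor curve, so the same death can count in more than one curve.
- **Line 1 type, clock at diagnosis or Line 1 start.** Women who began on something else are in the cohort only if they survived to a later CDK4/6 inhibitor. Once Line 1 has begun, women who began with the CDK4/6 inhibitor face no such condition.

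Curves labelled by treatment will be read as comparing treatments, even in a descriptive report. The only related caution, in Protocol 9.9, is about channeling: who is chosen for a treatment. It does not cover surviving long enough to receive one.

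**Working it through.** The documents give no OS figure, event count or power, so there is nothing to reproduce. The check asks how far the curves separate when treatment has no effect.

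**Inputs from the documents**
- Diagnosis from 01 January 2016 to 01 July 2021 (66 months) and cut-off 01 October 2021, giving 3 to 69 months of follow-up (SAP 2.1 and 4.1).
- Cohort below 30% of 180: 0.30 × 180 = 54, so fewer than 54 women (amendment tables of both documents).

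**Assumptions, not in the documents**
- One exponential death hazard for all women, median OS 36, 48 or 60 months.
- Uniform diagnosis dates.
- Exponential non-CDK4/6i Line 1 with median 14.5 months, followed by the CDK4/6 inhibitor. The 14.5 is the control-arm median PFS that Protocol section 7 cites from a trial, used as a stand-in. It is not a duration from this cohort.

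**1. Line 1 strata, clock at diagnosis (taken as Line 1 start).** Let D be death, L the end of Line 1 and C the cut-off. Women starting with a CDK4/6 inhibitor are all kept. The others are kept only if L < D and L < C.

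Hand check at median OS 48, ignoring the cut-off:
- S(36) = 0.5^(36/48) = 0.595
- P(L < D) = 48/(48 + 14.5) = 0.768
- P(D > 36 given L < D) = S(36) × [1 − (14.5/62.5) × 0.5^(36/14.5)] / 0.768 = 0.595 × (1 − 0.232 × 0.179) / 0.768 = 0.742

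With the cut-off included, simulation of one million women per setting gives Kaplan-Meier 3-year OS:

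| Assumed median OS | CDK4/6i first | Other first | Gap |
|---|---|---|---|
| 36 months | 50% | 64% | 14 points |
| 48 months | 59% | 72% | 12 points (59.4 v 71.7) |
| 60 months | 66% | 77% | 11 points |

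A separate set-up used median OS 24 to 48 months, Line 1 median 9 to 24 months and a mean of one month from diagnosis to Line 1. It gave gaps of 10 to 19 points between women starting with a CDK4/6 inhibitor and women starting with endocrine therapy. Starting the clock at Line 1 does not help: at median OS 36 and Line 1 median 15 months, the figures were 50.2% v 63.9%. Without the CDK4/6 inhibitor entry condition they were 50.2% v 50.0%, so that condition is the cause.

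**2. Ever-received strata.** The CDK4/6 inhibitor curve is then the whole cohort.
- Common hazard, median OS 48, chemotherapy start at a median of 24 to 36 months: 74 to 76% in the chemotherapy curve v 59% in the whole cohort.
- Chemotherapy given at progression (median 24 months), survival after progression median 18 months, death before progression median 200 months: 52% in the chemotherapy curve v 60% in the whole cohort. The direction reverses.

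**3. Cohort size.** Line 1 model at 54 women, median OS 48, assuming 25% start on something else before selection: that stratum averages 9 women, with 4 at risk at 36 months. The gap averages 13 points, with a 95% range of −31 to +47, and is zero or reversed in about 25% of runs.

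**4. After the fix.** With the clock at the first CDK4/6 inhibitor dose and strata fixed by then, 3-year OS by Line 1 type (CDK4/6i / endocrine / chemotherapy) is 49.9 / 49.8 / 49.9% against a true 50.0% at median OS 36, and 59.5 / 59.5 / 59.4% against 59.5% at median 48. The artefact disappears.

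**The case against.** **The deciding text may be redacted.** This stands. A reader might infer that the strata do depend on later treatment and that the curves will differ. The documents do not support that: the OS start and a stratum rule may lie in SAP 5.1 or 7.2, and neither can be called absent.

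**A third reading is sound.** This also stands. The type could mean the regimen begun with the CDK4/6 inhibitor, with the clock starting that day. The treatment labels in SAP 2.1 (palbociclib combination, CDK4/6 inhibitor) are compatible with that. If it is intended, the captions need only say so. The 3-year landmark named for OS in the endpoint tables might also mean a landmark analysis, but the visible plan is Kaplan-Meier in all patients. Under uniform diagnosis only 33 of 66 months of diagnoses allow three years of follow-up.

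**The direction is not fixed.** A reader might infer that the display must flatter treatments given before or after the CDK4/6 inhibitor. For ever-received strata this fails, as step 2 shows. A contrast with women never given chemotherapy would look larger, but neither caption specifies such a curve.

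**These may not be the only such curves.** A partly redacted sentence in SAP 7.2 allows differences by treatment type and line to be explored, so Figures 9 and 13 cannot be called the plan's sole OS comparison by treatment.

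**The analysis is exploratory, untested and small.** This limits the weight of the point but does not remove it. A small sample makes the gap noisy; it does not remove the bias. The protocol's warning addresses channeling only.

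**Conclusion.** The concern holds in a limited form. The visible plan stratifies OS by treatment type without tying the type to the OS start, in a cohort where women can receive several types and everyone must reach a CDK4/6 inhibitor at an unstated line. Two natural readings of that plan can produce separated curves with no treatment effect.

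The Line 1 artefact is about 11 to 14 points in 3-year OS. This rests on a common exponential death hazard, median OS of 36 to 60 months and a non-CDK4/6i Line 1 median of 14.5 months. No general size or direction can be given for ever-received strata. With fewer than 54 women, one observed gap could be far larger or have the opposite sign. Because OS is exploratory and descriptive, this should be corrected before the figures are produced; it does not threaten the primary objective.

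**What to change.** In the OS row of SAP 7.2.2 and in the captions of Figures 9 and 13, state the OS start and use only strata known on that date, with each woman in exactly one curve. One workable form starts the clock at the first CDK4/6 inhibitor dose and splits by the combination partner begun that day, or by line (first v later). It should not use both at once, because crossing them would leave too few women per curve in a cohort below 54, and fewer still in Figure 13. Otherwise, drop the treatment strata and show a single OS curve.

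The cost is wording in one table row and two captions. The dates needed are already on the extraction list: Protocol 9.3 includes "Systemic Therapies (therapy start and stop date including combination therapies, and line of therapy". The downside is that there would be no OS curve for chemotherapy or endocrine therapy alone, which a cohort defined by CDK4/6 inhibitor receipt cannot support. Channeling would remain, and the existing caution in Protocol 9.9 should stay.
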